Title of study:
Effectiveness of the Supportive and Palliative Care Review Kit (SPARK) for Cancer Patients in the Acute Hospital

NCT ID: not assigned

Date of document: 31 October 2017

Study protocol

Abstract

Introduction

There is a rising need for palliative care services in Singapore due to a rapidly ageing population and an increasing incidence of cancer. Current existing resources are inadequate – novel models of care are needed to expand access to palliative care without requiring significantly more specialist palliative care manpower.

Oncologist-driven referrals to a palliative care consultation service is the norm worldwide, including Singapore. This results in variable access to palliative care due to differences in referral practices. Palliative care involvement is also often delayed. In this study, we propose to test Supportive and Palliative care Review Kit (SPARK) – a novel integrated model of care in which the palliative care team co-rounds with the medical oncology team.

Specific Aims and Hypothesis

This study aims to evaluate the impact of SPARK compared to usual care. We hypothesize that SPARK will result in more advanced cancer patients having access to palliative care, and at the same time operate at lower net cost. We also hypothesize that the improved efficiency of SPARK will result in shorter hospital length of stay for stage 4 cancer patients.

Methods

A cluster randomized trial with step wedged design will be used to compare SPARK to usual care. Data will be collected on health services utilization and access to palliative care services. Net costs will also be compared between SPARK and usual care. Semi-structured interviews with patients and healthcare professionals will be used to explore differences in experiences of healthcare provision between both models of care.

Importance

Singapore has a rising prevalence of cancer patients who require palliative care input, but only a minority are able to access it at present. If the SPARK model of care proves to be a scalable and cost-effective way of expanding access to palliative care, more cancer patients can benefit from palliative care.

Specific aims and hypotheses

The overall aim of this proposed study is to evaluate the impact of the Supportive and Palliative care Review Kit (SPARK) model of care compared to usual care on health services utilization, access to palliative care, net costs and the experiences of both patients and healthcare providers. SPARK is an integrated palliative care and medical oncology co-rounding model of care for cancer patients in the acute hospital setting. We plan to develop and comprehensively assess this model using a prospective cluster randomized controlled trial and semi-structured interviews.

The study specific aims and hypotheses are:

Specific aim 1: To determine the effectiveness of SPARK on hospital length of stay (primary outcome) and other health service utilization metrics

Hypothesis: The SPARK model of care will reduce hospital length of stay compared to usual care, due to earlier involvement of palliative care in the course of hospital admission and consequently swifter relief of problems that prompted the hospitalization.

Other metrics of health service utilization will also be explored, including hospital-free days and visits to the Emergency Department in the last 6 months of life, and number of days to hospital readmission within 30 days.

Specific aim 2: To assess the relationship between the SPARK model of care and access to palliative care services

Hypothesis: The SPARK model will be associated with a greater proportion of cancer patients who receive any form of palliative care input during their hospital admission.

Background and significance

Palliative care, according to the World Health Organization, is an approach that improves the quality of life of advanced cancer patients and their families, through early identification, assessment and treatment of pain and other problems, physical, psychosocial and spiritual. (1) Concurrent palliative care and oncology care for advanced cancer patients results in improved quality of life, better symptom control and perhaps even longer survival. (2-7) International organizations recommend that palliative care should be integrated with oncology – the question that remains is how this integration should occur to optimize health outcomes. (7-9)

According to published literature, only 5-11% of stage 4 cancer inpatients in the acute hospital setting receive palliative care. (10, 11) Predominant models of care rely on direct delivery of care by specialist palliative care healthcare professionals, and there is insufficient manpower to extend this labor-intensive service to more cancer patients. (12) Even in resource-rich United States, the estimated gap between current supply and hypothetical demand is 6,000-18,000 individual physicians. (13, 14)

In Singapore, a rapidly ageing population and increasing incidence of cancer means a rising need for palliative care services that cannot be fully met by current models of care. (15-18) In the acute hospital setting, an unscheduled admission for a stage 4 cancer patient indicates that palliative care may be beneficial. (19) Our previous study showed that 84% of cancer inpatients had stage 4 cancer and that unscheduled admissions accounted for 82% of total admissions, yet only 21% received a palliative care review. (20) In recent years, anecdotal evidence suggests that home hospice services have been forced to restrict referrals and even close services temporarily to new referrals due to insufficient manpower. To extend palliative care services to more cancer patients, it will be inadequate to simply increase manpower within current service models – the need for large numbers of extra manpower cannot be met.

Singapore urgently needs a model of care that can expand access to palliative care for more cancer patients without requiring a lot more palliative care manpower. Therefore, the focus of our research is not whether palliative care improves patient outcomes – that has already been affirmed in recent research. The overall research question addressed by this proposed study is whether the SPARK model of care is a better way of delivering integrated palliative care to cancer patients in the acute hospital setting.

We propose a cluster randomized controlled trial to test the SPARK model of care for cancer inpatients in the acute hospital setting. This is novel in our institution because palliative care is currently delivered only as a separate consultation service – the most common model worldwide. (21) In the SPARK model, palliative care doctors and nurses are integrated with the oncology team, supporting them in their delivery of basic palliative care, seamlessly stepping in and out to deliver specialist palliative care directly to patients when needed. (22-25) With this approach, it is anticipated that there will be more efficient collaborative working between the oncology and palliative teams.

In the short term, our proposed study responds to an urgent need to expand access to palliative care for advanced cancer patients, in a model that does not require a large increase in specialist palliative care manpower. In the long term, scalable and effective models of care need to be developed for the exponentially rising need for palliative care in Singapore and across the world.

Methods

Study setting

The study will take place in Singapore General Hospital, a 1597-bedded acute hospital with more than 78,000 admissions per year. About 5,000 hospital admissions per year are cancer patients under the care of the Division of Medical Oncology (DMO), of which 80% are advanced cancer patients. This service is the largest public provider of cancer care in Singapore.

Current model of service

The current model of service is a consultation service with oncologist-driven referrals. A cancer patient admitted to hospital may have pain or other physical symptom problems such as breathlessness, or psychosocial and spiritual issues. The oncology team usually manages them first-line, and would refer to the palliative care team for further management only if the problems were unresolved after oncology management. Upon a referral from the oncologist, the palliative care team will review the patient and make suggestions for patient management, but the oncology team still takes primary responsibility for the patient's care. In the current model, about 20% of cancer inpatients are referred to the palliative care team.

The SPARK model of care

In the SPARK model of care, a specialist palliative care physician and nurse join the DMO team as integrated members. The patient's issues are managed collaboratively by the palliative care and oncology healthcare professionals. The form of palliative care provided will depend on the needs of individual patients and may include expert advice given to the oncology team, screening assessments for unidentified problems, or direct provision of palliative care for complex issues. It is anticipated that **more** patients admitted under the care of the integrated palliative oncology team will receive some varying degree of palliative care input as needed, whether directly or indirectly through support given to the oncology nurses and doctors.

Study design

Cluster-randomized trial with stepped-wedge design, unblinded due to practical challenges of blinding. There will be 4 teams (clusters) within the DMO inpatient service, each comprising a team of senior consultant physicians, middle level and junior doctors, and oncology nurses. This follows current team structures. During the intervention period, a palliative care physician and nurse will join the team as integrated members.

The study will be conducted over 20 months from January 2018 to August 2019, with each cluster crossing over from 'usual care' to 'spark intervention' at 4-month intervals. Each cluster will be randomly assigned a specific timing of crossing over.

Table 1

	Jan-Apr 2018	May-Aug 2018	Sep-Dec 2018	Jan-Apr 2019	May-Aug 2019
Cluster 1	control	intervention	intervention	intervention	intervention
Cluster 2	control	control	Intervention	intervention	intervention
Cluster 3	control	control	control	Intervention	intervention
Cluster 4	control	control	control	control	intervention

Study patients

All hospital admissions with stage 4 cancer under the care of the oncology team will be included.

Data collection

A waiver of individual patient consent will be sought for the collection of health services utilization data from the electronic health records, as this will present no more than minimal risk of harm to participants. Electronic health data will be kept confidential and stored in a secure location. All data will be anonymized prior to statistical analysis.

Patient quality of life, measured by patient questionnaires, will not be measured because this was found to be infeasible in our pilot study. In the inpatient hospital setting, patients were physically ill with acute problems such as pain, leading to low recruitment and data completion rate.

Specific aim 1: To analyze the effect of the SPARK model on hospital length of stay and health services utilization. The following data will be extracted from the electronic health records: dates of hospital admission and discharge for the index admission and all subsequent admissions, dates of all subsequent Emergency Department attendances, and date of referral to community palliative care services.

Specific aim 2: To determine the access to palliative care. The receipt of different forms of palliative care from the palliative care doctor/nurse will be recorded. This may include direct care as well as indirect input e.g. specific advice regarding medication dose for that particular patient or suggestion of an appropriate source of support in the community for the patient.

Data analysis

Specific aims 1 and 2: Mixed-effect linear regression will be used to compare differences in (log-transformed) length of stay (primary outcome) and hospital-free days in the last 6 months of life between 'spark intervention' and 'usual care' groups controlling for (team- and patient-level) clustering and time effect. (30) Similarly, mixed-effect logistic regression will be used to compare the proportion of patients who receive direct palliative care in the usual care model versus the SPARK model. A separate analysis will also be done for patients who receive any specific form of palliative care (direct or indirect).

Specific aim 3: A net cost analysis of SPARK will be undertaken from the perspective of the restructured health system. It is possible that total labour costs are greater for SPARK but that costs per patient are lower because SPARK allows for seeing more patients. This difference, whether positive or negative, represents differences in direct labour costs. Because this is a new model of care, this cost will not be reflected in the billing data. However, the billing data can be used to quantify other differences that may result from SPARK, such as savings through reductions in length of stay. Using the billing data, we will again quantify total and per capita cost differences between SPARK and usual care. The net costs of SPARK will be quantified by adding per capita labour cost differences to per capita billing cost differences. If negative, then SPARK is cost saving. If positive, then SPARK is more expensive.

Sample size calculation

It is estimated that each of the 4 clusters will have an average of 300 stage 4 cancer patient admissions per 4-month period, giving a total of 6000 admissions over the 20-month study period.

Based on results from our pilot study, we estimated the mean hospital length of stay to be about 6 days and the standard deviation to be 7. We estimated the intra-cluster coefficient arising from multiple admissions per person to be 0.2 and that each patient would have an average of 2 admissions during the study period. Therefore, the design effect arising from multiple admissions per person is 1.2 and 300 patient admissions would give an “effective sample size” of 250 admissions per 4-month period, or a total “effectiveness sample size” of 5000 admissions over the study period. Assuming the coefficient of variation between clusters to be about 0.25, the sample size of totally 6000 admissions as aforementioned would provide 80% power at 5% two-sided type 1 error rate to detect a mean difference of 1 day in hospital length of stay in the stepped-wedge design in table 1. (31)

References

1. WHO Definition of Palliative Care. <http://www.who.int/cancer/palliative/definition/en/> (last accessed 3 January 2017)

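### Stays ending in death are not distinguished from live discharges, so a difference in length of stay cannot by itself be attributed to swifter relief

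*Protocol*

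**What the plan says.** - **Population** (Protocol, Study patients): "All hospital admissions with stage 4 cancer under the care of the oncology team will be included". No exception is made for stays that end in death.
- **Data** (Protocol and SAP, Data collection, Specific aim 1): "dates of hospital admission and discharge for the index admission and all subsequent admissions", plus dates of later Emergency Department attendances and of referral to community palliative care. Discharge status, discharge destination and date of death are not listed.
- **Model** (Protocol and SAP, Data analysis, Specific aims 1 and 2): a mixed-effect linear regression on log length of stay, controlling for team- and patient-level clustering and for time. No censoring, competing event or sensitivity analysis for death is described.
- **Hypothesis** (Protocol, Specific aim 1): SPARK will shorten the stay "due to earlier involvement of palliative care in the course of hospital admission and consequently swifter relief of problems that prompted the hospitalization".
- **Where death does appear**: a secondary outcome is "hospital-free days in the last 6 months of life", which can be computed only with a date of death. The Protocol's background says that concurrent palliative care brings "improved quality of life, better symptom control and perhaps even longer survival".

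**The concern.** Every admission is included, the stay is the gap between two dates, and a linear model cannot censor. A stay that ends in death therefore enters as a completed stay, and an early death counts as a short one. The only alternative is to drop such stays, which would contradict the inclusion rule.

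The population is entirely stage 4, and by the Protocol's own account palliative care may affect survival. Through community referral it might also affect where patients die. Deaths in hospital therefore need not be balanced between conditions. No other planned measure can check the mechanism: quality-of-life questionnaires were ruled out as infeasible, and no symptom or in-hospital mortality outcome is planned. What is at stake is the explanation attached to the primary result, in either direction.

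**Working it through.** **Inputs from the documents** (Sample size calculation): mean stay 6 days, SD 7; 4 teams, 5 periods, 250 effective admissions per team-period (300/1.2); between-team coefficient of variation 0.25, so τ = 0.25 × 6 = 1.5 days; target difference 1 day; 80% power; two-sided 5%.

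**Assumptions, not in the documents:** the share of stays ending in death (5% to 25%) and how SPARK changes those stays.

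**1. The plan's own figure.** Hussey-Hughes variance with I = 4, T = 5, U = 10, W = 30, V = 30, s² = 49/250 = 0.196, τ² = 2.25:

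Var = I·s²·(s² + T·τ²) / [(I·U − W)·s² + (U² + I·T·U − T·W − I·V)·τ²]
= 4 × 0.196 × 11.446 / (10 × 0.196 + 30 × 2.25)
= 8.974 / 69.46 = 0.1292

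SE = 0.359 day. Power = Φ(1/0.359 − 1.96) = 79.4%, which agrees with the stated 80%. The calculation uses one mean and SD for all stays and makes no provision for death.

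**2. Day-scale illustration.** Suppose only fatal stays shorten, by an assumed 3 days, and live discharge is unchanged. The fall in mean stay is share × 3. The chance of significance in either direction is Φ(d/SE − 1.96) + Φ(−d/SE − 1.96), which is 5% when d = 0.

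| Share ending in death | Fall in mean stay (days) | Chance of p < 0.05 |
|---|---|---|
| 5% | 0.15 | 7% |
| 10% | 0.30 | 13% |
| 20% | 0.60 | 39% |

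**3. The planned log scale.** Log variance = ln(1 + 49/36) = 0.859; team variance on the log scale = ln(1 + 0.25²) = 0.0606. The same formula gives SE = 0.048. Take a 20% share and let fatal stays shorten proportionally from an average of a days to a − 3. The mean log change is 0.20 × ln((a − 3)/a).

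| a (days) | Mean log change | Chance of a significant reduction |
|---|---|---|
| 6 | −0.139 | 83% |
| 9 | −0.081 | 40% |
| 12 | −0.058 | 23% |
| 15 | −0.045 | 15% |

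The same 3-day cut thus gives anything from 15% to 83%, depending on a quantity that the documents do not supply.

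**4. Direction.** A simulation set lognormal time to live discharge against exponential time to death, calibrated to mean 6 and SD 7. The discharge process was held fixed and only the hazard of in-hospital death was changed.

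| Share ending in death | Hazard ratio 0.8: change in mean (days) | Hazard ratio 1.5: change in mean (days) | Hazard ratio 1.5: chance of p < 0.05, log scale |
|---|---|---|---|
| 5% | +0.07 | −0.17 | 8% |
| 10% | +0.15 | −0.33 | 15% |
| 20% | +0.30 | −0.61 | 41% |
| 25% | +0.38 | −0.75 | 54% |

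**5. Could death alone produce the whole 1-day fall?** With constant hazards, moving the mean from 6 to 5 days multiplies the total exit hazard by 1.2. If deaths make up a share d of exits and the discharge hazard is unchanged, 1 − d + d·HR = 1.2, so HR = 1 + 0.2/d. That is 5.0, 3.0, 2.0 and 1.8 at d = 5%, 10%, 20% and 25%.

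**The case against.** The strongest reply is that length of stay is presented as a health-service-utilization measure, and the Protocol's net cost analysis (Data analysis, Specific aim 3) looks to reduced stay for savings. For bed use, how a stay ends does not matter. The hypothesis itself is only that stay will fall; swifter relief is the reason offered, and the Abstract offers improved efficiency as another. This stands: a reader might infer that the primary outcome is invalid, and the documents do not support that.

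A reader might also infer that the trial could never separate deaths from discharges. That goes too far. Date of death is needed for the outcomes counted back from death, and set against the discharge date it would identify in-hospital deaths. The extraction list is evidently incomplete, since it omits that date. What is missing is a pre-specified analysis, not the possibility of one.

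Nor do the documents suggest that deaths would favour SPARK. Their only statement on survival points to longer life, which could lengthen stays and conceal a benefit. The 3-day cut has no source. The significance chances are not false-positive rates either, because mean stay really does fall in those scenarios.

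Finally, live discharge is not relief. A transfer to die elsewhere also counts as a live discharge, so a competing-event analysis alone cannot settle the mechanism. That is a reason to record destination and not to make that analysis a formal gate. None of these replies removes the gap: under the plan as written, the stated explanation remains mixed with any change in in-hospital death.

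**Conclusion.** The point holds as a cheap improvement to interpretation. The primary analysis remains valid for bed use and cost, but a difference in stay, or its absence, cannot on its own be credited to or held against swifter relief.

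The size is unknown. The day-scale illustration gives a fall of 0.15 to 0.60 day, or 15% to 60% of the 1-day target, and rests entirely on an assumed death share of 5% to 20% and an assumed 3-day cut. On the planned log scale the effect depends heavily on how long fatal stays last. The bias can run either way. To conclude that deaths could readily account for a full 1-day reduction would be too strong: under constant hazards that needs the in-hospital death hazard to rise 1.8-fold to 5-fold across death shares of 25% down to 5%.

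**What to change.** Keep the primary analysis and state that stays ending in death enter it as stay to any exit. Then:

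1. Add discharge status and destination to the extraction list, together with the date of death that the end-of-life outcomes already require.
2. Pre-specify two supporting analyses: (a) in-hospital death by condition, using the mixed logistic model already planned for access to palliative care; (b) time to live discharge with in-hospital death as a competing event, with team and period effects and allowance for repeat admissions by the same patient (the plan assumes 2 per patient on average, with a coefficient of 0.2).
3. Report destination, for example home or hospice, by condition, so that transfers before death are visible.
4. Use (a) and (b) to interpret the primary result, not as a formal gate; the trial has not been powered for them. If they do not support earlier live discharge, limit the conclusion to bed use.

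The cost is one or two extra fields from the same electronic record, two extra models, and a more cautious conclusion if they disagree with the primary result. Randomisation, sample size and the primary model do not change.

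### The net cost rule leaves its per capita denominator undefined; on the reading its rationale most naturally suggests, the labour term can be negative while total labour spending rises

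*Protocol*

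**What the plan says.** The net cost method appears only in the Protocol, Data analysis, under Specific aim 3. It takes the perspective of the health system and allows that "total labour costs are greater for SPARK but that costs per patient are lower because SPARK allows for seeing more patients". It continues: "This difference, whether positive or negative, represents differences in direct labour costs". It notes that SPARK's own labour will not show in billing data because the model is new. For billing, "we will again quantify total and per capita cost differences between SPARK and usual care". Net cost is then found by "adding per capita labour cost differences to per capita billing cost differences"; a negative sum is read as cost saving and a positive sum as more expensive.

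No denominator is given for either term, and the staff whose labour counts are not named. The SAP's Data analysis section covers aims 1 and 2 only, so it does not settle either point.

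Other sections bear on the choice:

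- Study patients: "All hospital admissions with stage 4 cancer under the care of the oncology team will be included".
- Sample size calculation: "each of the 4 clusters will have an average of 300 stage 4 cancer patient admissions per 4-month period", and "each patient would have an average of 2 admissions during the study period".
- Study design describes the oncology teams as "each comprising a team of senior consultant physicians, middle level and junior doctors, and oncology nurses"; a palliative care physician and nurse join them under SPARK.
- Current model of service puts palliative referral at about 20% of cancer inpatients. The SPARK model of care expects more patients to receive input but gives no figure.

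**The concern.** The rationale is not a side remark: the sentence after it makes that difference the labour component. A cost per patient that falls because more patients are seen measures how efficiently palliative staff are used. It does not measure what the health system spends on the admissions in the trial. Billing and length-of-stay savings, by contrast, arise over all included stage 4 admissions, so admissions are the natural billing denominator (an inference, since the text does not say). Adding the two would mix denominators, and the sign of the sum could then differ from the sign of the real change in spending.

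Lower net cost is a stated hypothesis in the Abstract, which ties wider use of SPARK to its proving scalable and cost-effective. A wrong sign would therefore matter, although this is not the primary outcome. A larger sample would not correct it, and an open denominator can be chosen after the results are known.

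**Working it through.** **The plan's own figures.** The documents give no number for net cost. The admission count reproduces: 4 clusters × 5 periods × 300 = 6000. In Table 1 the control team-periods are 1 + 2 + 3 + 4 = 10 and the SPARK team-periods 4 + 3 + 2 + 1 = 10, so 10 × 300 = 3000 expected admissions in each condition.

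**Does the rationale fit a per-admission denominator?** With 3000 admissions in each condition, labour per admission is total labour / 3000 in both. If the total is higher under SPARK, so is the per-admission figure. Total up with cost per patient down therefore needs a denominator that grows under SPARK. Patients seen by palliative care is the one the protocol describes.

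**Inputs.**

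- p0, proportion seen under usual care: 20% of cancer inpatients (Current model of service). If everyone referred has advanced disease, it is 0.20/0.80 = 25% of stage 4 admissions. The Background figures agree: 0.21/0.84 = 25%.
- p1, proportion seen under SPARK: not in the documents; assumed 30% to 100%.
- R, ratio of SPARK to usual-care total palliative labour at equal admissions: not in the documents; assumed.
- Usual-care palliative labour is set at 100 per admission.

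**Formulas.**

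- Labour term per admission: 100 × (R − 1).
- Labour term per patient seen: 100 × (R/p1 − 1/p0).
- The second is negative while the first is positive when 1 < R < p1/p0.

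**Upper limit on R for a reversed sign (p1/p0).**

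| p1 (assumed) | p0 = 20% | p0 = 25% |
|---|---|---|
| 30% | 1.5 | 1.2 |
| 60% | 3.0 | 2.4 |
| 100% | 5.0 | 4.0 |

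**One illustration.** Take R = 2, p0 = 20%, p1 = 60%.

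- Per admission: 100 × (2 − 1) = +100.
- Per patient seen: 100 × (2/0.60 − 1/0.20) = 333 − 500 = −167.
- Let B be the billing difference per admission. The rule calls SPARK cost saving for any B below +167; spending per admission falls only if B is below −100. The call is wrong for B between −100 and +167, which includes no billing saving at all.

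**The error can run the other way.** With R = 2, p0 = 25%, p1 = 30%, the term is 100 × (2/0.30 − 1/0.25) = 667 − 400 = +267 against a correct +100. A billing saving between 100 and 267 would then be wrongly called more expensive.

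**Readings that avoid the reversal.**

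- Both terms over all included admissions: the labour term is 100 × (R − 1), always with the sign of the total.
- Whole-team labour over all admissions: if palliative staff are a share s of usual-care team labour, the team ratio is 1 + s(R − 1). With s = 5% to 20% (assumed) and R = 2 it is 1.05 to 1.20, a term of +5 to +20 per 100 of team labour, the correct sign.
- Throughput: if stay fell from 6 to 5 days and every freed bed were refilled (an upper bound), admissions would rise by 6/5 = 1.2. Whole-team labour per admission would change from 1.05/1.2 − 1 = −12.5% to 1.20/1.2 − 1 = 0%. That fall is genuine per admission, with matched denominators, although total labour is higher.

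**Both terms per patient seen.** The denominators match, but the patients do not. Under usual care the palliative team is called when problems remain after oncology management; under SPARK the input also includes screening and advice. A difference in cost per patient seen then partly reflects who is seen.

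**The case against.** The strongest reply is that the text can be read as sound. The word *again* in the billing sentence puts billing on the same footing as labour, and the two are then added, which suggests one denominator. The rationale is worded as a possibility, not as a definition. The 300 admissions per team-period is a planning average, not a forecast by condition, and the same paragraph mentions length-of-stay savings, so seeing more patients could mean throughput. Total differences are also planned and would probably show higher spending. Finally, the public text looks shortened: the aims section lists only aims 1 and 2, and references 26 to 29 are listed but not cited. A fuller version may define these terms.

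Most of this stands as a limit on the claim. A reader might infer that the plan has committed to mixed denominators, or that the trial will wrongly declare a saving. The documents support neither: the reversal needs one reading of the text plus values of R and p1 that they do not give. If R is at or above p1/p0, the sign is right, although the size is generally still wrong.

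What does not stand is that nothing needs changing. The plan's rationale fits poorly with a per-admission denominator at the admissions it expects, and matching both terms on patients seen compares different groups. The totals are only a partial safeguard because the decision rule uses the per capita sum.

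**Conclusion.** The concern holds in conditional form. The public text defines neither the per capita denominators nor the labour counted. On the reading that its rationale most naturally suggests, the labour term is negative despite higher total palliative labour whenever 1 < R < p1/p0. With p0 at 20% to 25% and p1 assumed at 30% to 100%, the upper limit on R is 1.2 to 5. The protocol's expectation that SPARK will not need a large increase in specialist manpower makes modest values of R plausible but fixes none. The figures show the mechanism and do not predict the error; its direction and size cannot be known in advance.

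Confidence is medium, because other readings largely or wholly remove the reversal. The aim is not primary and the correction is cheap, so this should be fixed but does not threaten the main analysis.

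**What to change.** Add to the cost analysis, and carry into the SAP:

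1. Labour and billing costs are both divided by all included stage 4 admissions in each condition, whether or not the patient was seen by palliative care.
2. The staff groups counted and the source of the labour data are named for both conditions.
3. Usual-care consultation labour already in billing is left out of the labour term, so that it is not counted twice.
4. The total net cost difference (labour plus billing) is reported beside the per-admission result. This captures any change in the number of admissions, which a per-admission figure alone would miss. Cost saving is claimed only if the two agree.
5. Labour cost per patient seen is reported only as a separate efficiency figure and is not added into net cost.

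Naming admissions as the unit also settles whether per capita means per person or per admission, about a factor of 2 at the planned two admissions per patient.

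The cost is a few sentences and a little more analysis work. The documents describe no labour data source, so item 2 may need some collection if whole-team labour is chosen. The labour component may look less favourable to SPARK.
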